8.3.9 Raynaud's Condition Score (RCS) (MCTD participants only)

The Raynaud's Condition score (RCS) is participant's rating of difficulty considering number of attacks, duration, amount of pain, numbness, or other symptoms caused in the fingers (including painful sores) due to the Raynaud's phenomenon and impact of Raynaud's alone on use of hands every day. An 11 point Likert scale is used to rate the difficulty caused by the condition with 0 = no difficulty and 10 = extreme difficulty. Participants are asked to select the number that best describes their difficulty, with higher score indicating worse condition.

RCS will be completed by the study participants with MCTD at the study site as per study assessment schedule (Table 8-1).

8.3.10 King's Brief Interstitial Lung Disease (K-BILD) (MCTD participants only)

The K-BILD questionnaire is a self-administered health-status questionnaire that has been developed in patients with interstitial lung diseases. It consists of 15 items in three domains: i) breathlessness and activities, ii) psychological factors, and iii) chest symptoms. Domain and total scores range from 0 to 100, with higher scores representing better health status (Patel et al 2013; Sinha et al 2019; Nolan et al 2019; Flaherty et al 2019).

K-BILD will be completed by the study participants with MCTD at the study site as per study assessment schedule (Table 8-1).

8.3.11 Sjögren's Tool for Assessing Response (STAR)

STAR is a composite responder index, including in a single tool all main disease features, and designed for use as a key efficacy endpoint in SjS randomized clinical trials (Seror et al 2022).

In this study lacrimal gland function will be assessed using the Schirmer's test, while ocular staining score will not be used to calculate STAR response. Further, the biological domain will be assessed using IgG, while rheumatoid factor (RF) will not be used to assess STAR response.

Domain	Point	Definition of response			
Systemic activity	3	Decrease in clin ESSDAI ≥ 3 points			
Patient reported outcome	3	Decrease in ESSPRI ≥ 1 point or 15%			
Lacrimal gland function (assessed by Schirmer's test)	1	If abnormal score at baseline: increase ≥ 5 mm from baseline If normal score at baseline: no change to abnormal			
Salivary gland function (assessed by unstimulated salivary flow)	1	increase ≥ 25% from baseline			
Biological (assessed by serum IgG levels)	1	Decrease ≥ 10%			

Table 8-3STAR response criteria used in the study

STAR responder ≥ 5 points

8.3.12 Appropriateness of efficacy assessments

Efficacy measures in this study are primarily based on ESSDAI measuring organ-specific disease criteria, and on ESSPRI measuring the patient's subjective disease impact. Both instruments are widely accepted and validated, gold-standard measures of systemic and symptomatic manifestations of SjS, respectively.

ESSDAI is a systemic disease activity index that classifies disease activity in 3-4 levels, over each of 12 differentially weighted domains (biologic, hematologic, articular, glandular, cutaneous, constitutional, lymphadenopathy, renal, pulmonary, PNS, CNS and muscular). A composite weighted score provides an accurate assessment of disease activity, with a good sensitivity to change, as validated in multiple cohort studies (Seror et al 2015a). The ESSPRI tool, on the other hand, is a patient reported composite score of symptoms of dryness, limb pain and fatigue evaluated on 0-10 visual analog scale, during the preceding 2 weeks (Seror et al 2011). Patient reported scores have poor sensitivity to change in disease activity, but among available tools, ESSPRI has been reported to have significantly better sensitivity. A recent prospective study reported poor correlation between systemic and patient scores, suggesting that the two indices evaluate complementary components of disease activity, therefore underscoring the importance of evaluation of both parameters to arrive at an accurate assessment of disease activity and change thereof (Seror et al 2015b).

8.4 Safety

Safety assessments are specified below with the assessment schedule detailing when each assessment is to be performed.

For details on AE collection and reporting, refer to AE section.

As per Section 4.6, during a Public Health emergency as declared by Local or Regional authorities i.e. pandemic, epidemic or natural disaster, that limits or prevents on-site study visits, regular phone or virtual calls can occur (every 4 weeks or more frequently if needed) for safety monitoring and discussion of the participant's health status until it is safe for the participant to visit the site again.

 Table 8-4
 Assessments & Specifications

Assessment	Specification
Physical	A complete physical examination will include the examination of general appearance, skin, neck (including thyroid), eyes, ears, nose, throat, lungs, heart, abdomen, back, lymph nodes, extremities, vascular, and neurological. If indicated based on medical history and/or symptoms, rectal, external genitalia, breast, and/or pelvic exams may be performed.
	The investigator should ask the participant for and pay attention to presence of signs and symptoms of infection.
	Information for all physical examinations must be included in the source documentation at the study site. Clinically relevant findings that are present prior to signing informed consent must be recorded on the appropriate CRF that captures medical history. Significant findings made after signing informed consent which meet the definition of an Adverse Event must be recorded as an adverse event.

Assessment	Specification
Vital signs	Vital signs will include the collection of otic or oral body temperature (recorded in °C), blood pressure (BP) and pulse measurements.
	After the participant has been sitting for 3 minutes, with back supported and both feet placed on the floor, systolic and diastolic BP will be measured using an automated validated device, e.g. OMRON with an appropriately sized cuff. In case the cuff sizes available are not large enough for the participant's arm circumference, a sphygmomanometer with an appropriately sized cuff may be used.
	In case of repeated vital assessments, the eCRF should contain all the results.
	Clinically notable vital signs are defined in Section 16.1.
Height and weight	Height in centimeters (cm) and body weight (to the nearest 0.1 kilogram (kg) in indoor clothing, but without shoes) will be measured.

8.4.1 Laboratory evaluations

A central laboratory will be used for analysis of all safety specimens collected. Details on the collection, shipment of samples and reporting of results by the central laboratory are provided to investigators in the central laboratory manual.

Urinalysis

A midstream urine sample (approx. 30 mL) will be obtained, in order to avoid contamination with epithelial cells and sediments, and to allow proper assessments.

All abnormal lab results must be evaluated for criteria defining an adverse event and reported as such if the criteria are met. For those lab adverse events, repeated evaluations are mandatory until normalization of the result(s) or until the result is no longer considered to be clinically significant.

Clinically notable laboratory findings are defined in Section 16.1.

Test Category	Test Name
Hematology	Hematocrit,
	Hemoglobin,
	Ery. Mean Corpuscular Hemoglobin,
	Ery. Mean Corpuscular HGB Concentration,
	Ery. Mean Corpuscular Volume,
	Platelets,
	Erythrocytes,
	Leukocytes,
	Differential (Basophils, Eosinophils, Lymphocytes, Monocytes, Neutrophils, Bands),
	Immunoglobulins quantitative (IgG, IgA, IgM, IgE),
	Ccomplement (C3, C4, CH50)

 Table 8-5
 Laboratory evaluations

Novartis Amended Protocol Version v03 (Clean)

Test Category	Test Name
Chemistry	Albumin,
	Alkaline phosphatase,
	ALT,
	AST,
	Gamma-glutamyl-transferase (GGT),
	Lactate dehydrogenase (LDH),
	Bicarbonate,
	Calcium,
	Chloride,
	Sodium,
	Potassium,
	Creatinine,
	eGFR,
	Cystatin C,
	Creatine kinase,
	Total Bilirubin (if elevated above 1.5x, Direct Bilirubin and Indirect Bilirubin will be differentiated),
	Total Cholesterol,
	Total Protein,
	Triglycerides,
	Urea Nitrogen or Urea,
	Uric Acid,
	Amylase,
	Lipase,
	Glucose (non-fasting),
	CRP,
Commerc	cially Confidential Information
Urinalysis	Microscopic Panel (Erythrocytes, Leukocytes, Casts, Crystals, Bacteria, Epithelial cells)
	Macroscopic Panel (Dipstick) (Color, Bilirubin, Macroscopic Blood, Glucose, Ketones, Leukocytes esterase, Nitrite, pH, Protein, Specific Gravity, Urobilinogen)
Coagulation	Prothrombin time (PT),
	International normalized ratio [INR]),
	Activated partial thromboplastin time (APTT)
Serology (Hepatitis and HIV)	Hepatitis B Virus Surface Antigen (HBsAg),
	Hepatitis B Virus core antibody (Anti-HBcAb),
	Hepatitis B Virus DNA (HBV DNA),
	Hepatitis C Virus Antibody (HCV),
	Hepatitis C Virus RNA (HCV RNA),
	HIV Ab
Pregnancy Test	Serum / Urine pregnancy test

8.4.2 Electrocardiogram (ECG)

ECGs will be collected at the site and evaluated centrally.

Single 12-lead ECGs will be recorded at each study visit.

Full details of all procedures relating to the ECG collection and reporting are contained in the technical manual provided by the core laboratory.

Electrocardiograms (ECGs) must be recorded after 10 minutes rest in the supine position to ensure a stable baseline. The Fridericia QT correction formula (QTcF) will be used for clinical decisions.

All ECGs, including unscheduled safety ECGs with clinically relevant findings collected during the study need to be transmitted to the central ECG laboratory for review.

Additional, unscheduled safety ECGs may be repeated at the discretion of the investigator at any time during the study as clinically indicated. For any ECGs with participant safety concerns, two additional ECGs must be performed to confirm the safety finding. ECG safety monitoring, or a review process, should be in place for clinically significant ECG findings before administration of study treatment and during the study.

Clinically significant abnormalities must be recorded on the CRF as either medical history/current medical conditions or adverse events as appropriate.

8.4.3 **Pregnancy and assessments of fertility**

All pre-menopausal women who are not surgically sterile will have pregnancy testing. Additional pregnancy testing might be performed if requested by local requirements. Serum pregnancy testing is required at screening and the follow up visit. During the study, urine pregnancy testing should be done at monthly intervals. The positive urine test needs to be confirmed with serum test. If positive, the participant must be discontinued from study treatment.

Local pregnancy test and associated results will not be collected on CRF.

If participants cannot visit the site to have serum pregnancy tests during a Public Health emergency as declared by Local or Regional authorities i.e. pandemic, epidemic or natural disaster, that limits or prevents on-site study visits, urine pregnancy test kits may be used. Relevant participants can perform the urine pregnancy test at home and report the result to the site. It is important that participants are instructed to perform the urine pregnancy test first and only if the test result is negative proceed with the administration of the study treatment. A communication process should be established with the participant so that the Site is informed and can verify the pregnancy test results (e.g., following country specific measures).

Assessments of fertility

Medical documentation of oophorectomy, hysterectomy, or tubal ligation must be retained as source documents. Subsequent hormone level assessment to confirm the woman is not of child-bearing potential must also be available as source documentation in the following cases:

- 1. Surgical bilateral oophorectomy without a hysterectomy
- 2. Reported 12 months of natural (spontaneous) amenorrhea with an appropriate clinical profile.

In the absence of the above medical documentation, FSH (Follicle Stimulating Hormone) testing is required of any female participant regardless of reported reproductive/menopausal status at screening.

8.4.4 Appropriateness of safety measurements

The safety assessments selected are standard for this indication/participant population.

8.5 Additional assessments

8.5.1 Pharmacokinetics

PK blood samples will be collected at the visits and time points defined in the assessment schedule (Table 8-1). Instructions outlined in the laboratory manual regarding sample collection, numbering, processing and shipment should be followed.

Commercially Confidential Information

PK samples will be obtained in all participants. They will be evaluated in all participants, except the placebo group. From those blood samples, plasma will be prepared and plasma concentrations over time of MHV370 will be determined by a validated LC-MS/MS method with an anticipated Lower Limit of Quantification (LLOQ) of 1.0 ng/mL. Concentrations will be expressed in mass per volume units (ng/mL) and will refer to the free base. Concentrations below the LLOQ will be reported as "zero" and missing data will be labeled as such in the Bioanalytical Data Report.

In the optional case of further exploratory assessment (e.g. investigation of metabolites), a non-validated method will be used and results will be provided in a separate standalone report.

For standard PK abbreviations and definitions see the list provided in Section 12.5.3.

The following PK parameters at steady-state after 4 weeks of b.i.d. treatment will be determined from the plasma concentration time data using the actual recorded sampling times and non-compartmental method(s) with Phoenix WinNonlin (Version 6.4 or higher): Cmax, Tmax, AUClast. Additional PK parameters may be added to further characterize the dose/exposure relationship or refine PK/PD analysis. In addition, concentrations of MHV370 at selected time points will be characterized at Week 12 and Week 24.

Novartis	
Amended Protocol Version v03 (Clean)	

Commercially Confidential Information

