Treatment period lasts for 24 weeks, from Day 1 to Week 24 (Day 169). On Day 1, participants will be randomized to the respective SjS or MCTD treatment arms. Commercially Confidential Information

Participants will return to the site at approximately 4-weekly intervals. As MHV370 is administered for the first time in patients with SjS and MCTD, an additional visit will be performed at Week 2 (Day 15) for safety and compliance purposes.

Commercially Confidential Information

The PK assessments will be performed pre dose and at various time points post dose (until 4 h after dosing) at Week 4, Week 12 and Week 24. At Week 4, an additional PK sample will be taken at 6 hours post dose, at selected sites.

Additionally, as per the Assessment Schedule (Table 8-1), participants with SjS will:

- undergo ESSDAI, salivary flow rate and Schirmer's test assessments
- complete ESSPRI assessments

and participants with MCTD will:

- undergo ESSDAI (articular and pulmonary domains only), local spirometry, DLCO test Commercially Confidential Information
- complete RCS and K-BILD assessments

Commercially Confidential Information

On the visit days, participants will be asked to take their morning dose of the study drug at the site. Participants will return their used drug supply packs for compliance and accountability assessment and will receive a new supply of study drug for the next 4-week treatment period.

Each week, participants will be asked to complete diaries to record the administration of treatment.

All study visits will be ambulatory, however, for logistical reasons, it may be necessary for participants to come to the site the evening before their scheduled assessment visit. In these instances, the participants may stay overnight at the site, but this would not be considered a hospital admission.

Participants may be contacted by the Investigator/site staff during the study to ensure compliance/monitor safety by telephone or other means, if it is deemed appropriate or necessary by the Investigator.

The primary endpoint of the study will be assessed after the completion of 24-week treatment (Day 169; Week 24 visit).

Follow up and End of Study visit (EoS)

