Days	-42	1	15	29						57	85		113	141	169		199
Weeks	-6	0	2	4						8	12		16	20	24		28
Time (post-dose)	-	-	-	0h	0.5h	1h	2h	4h	6h	-	0h	4h	-	-	0h	4h	-
Body Weight	Х	Х		Х						Х	Х		Х	Х	Х		Х
PhGA - VAS		Х		Х						Х	Х			Х	Х		
FACIT-Fatigue		x		Х						х	Х			Х	х		
Hematology	Х	x	X	Х						Х	Х		Х	Х	Х		Х
Clinical Chemistry	Х	Х	X	Х						Х	Х		Х	Х	Х		Х
Coagulation Panel	Х	Х	X	Х						Х	Х		Х	Х	Х		Х
Urinalysis	Х	Х		Х						Х	Х		X	Х	Х		X
PK blood collection				X ²	Х	Х	Х	Х	X ³		X ²	Х			X2	Х	
Electrocardiogram (ECG)	Х	х	x	х						х	Х		х	х	х		Х
Patient diary (paper)					,					S		•					

Novartis	
Amended Protocol Version v03 (Clean)	

Page 57 of 105 Protocol No. CMHV370A12201

Period	Screening		Treatment													Follow up	
Visit Name	Screening	Baseline / Day 1	Week 2		Week 4				Week 8 Week 12			Week 16	Week 20	Wee	k 24	EOS	
Days	-42	1	15			2	9			57	8	5	113	141	16	69	199
Weeks	-6	0	2		4					8	1:	2	16	20	24		28
Time (post-dose)	-	-	-	0h					-	0h	4h	-	-	0h	4h	-	
					Coi	mme	rciall	ly Co	nfide	ential Inf	ormatio	on					
Pregnancy and assessments of fertility ^{6,7}	х	s		S						s	S		S	S	S		x
Study completion information																	х
Concomitant medications		X															
Adverse Events										Х							
		-				ļ	Asses	smen	ts spe	ecific to Sj	S						
ESSDAI	Х	Х		Х						X	Х			Х	Х		
ESSPRI		Х		Х						X	Х			Х	Х		
Anti-Ro/SSA (screening test)	Х																
Schirmer's test	Х	Х		Х							Х				Х		
Salivary flow rate (unstimulated)	Х	x		х							Х				Х		
						As	ssess	ments	spec	cific to MC	TD						
Anti-U1-RNP (screening test)	Х																
Local spirometry (FVC/FEV)		x									Х				Х		
DLCO		Х									Х				Х		

Novartis	
Amended Protocol Version v03 (Clean)	

Page 58 of 105 Protocol No. CMHV370A12201

Period	Screening		Treatment									Follow up					
Visit Name	Screening	Baseline / Day 1	Week 2		Week 4			Week 8	Week 12		Week 16	Week 20	Week 24		EOS		
Days	-42	1	15	29			57	8	5	113	141	10	69	199			
Weeks	-6	0	2	4			8	12	2	16	20	2	4	28			
Time (post-dose)	-	-	-	0h	0.5h	1h	2h	4h	6h	-	0h	4h	-	-	0h	4h	-

Commercially Confidential Information

ESSDAI ⁸	Х	X	X			Х	Х		Х	
Raynaud's Condition score	х	х	x				х		х	
K-BILD questionnaire	х	х	x			х	Х		х	

^x Assessment to be recorded in the clinical database or received electronically from a vendor ^s Assessment to be recorded in the source documentation only

¹ HBsAg and HBV DNA monitoring: only required for anti-HBc positive patients

² Pre-dose

³ Only at selected sites

Commercially Confidential Information

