2.8 Pharmacokinetic endpoints

PK Parameters

All participants within the PK analysis set will be included for the PK analyses.

MHV370 PK plasma concentration data will be listed by treatment group, participant and visit/sampling time point. Descriptive summary statistics for PK concentration data will be provided by treatment group and sampling time point, including the frequency (n, %) of concentrations below the lower limit of quantification (LLOQ) and reported as zero. Summary statistics will include mean (arithmetic and geometric), SD, CV (arithmetic and geometric), median, minimum and maximum. Concentrations below LLOQ will be treated as zero in summary statistics and for PK parameter calculations.

PK parameters will be listed by treatment group, visit/time and participant. Descriptive summary statistics for pharmacokinetic parameters will be provided by treatment separately and combined for SjS and MCTD subjects. Summary statistics include mean (arithmetic and geometric), SD, and CV (arithmetic and geometric), median, minimum, and maximum. An exception to this is Tmax where median, minimum, and maximum will be presented.

AUClast	The AUC from time zero to the last measurable concentration sampling time (tlast) (ng x h / mL) $$
AUC0-t	The AUC from time zero to specified time t (ng x h / mL)
AUCtau	The AUC calculated to the end of a dosing interval (tau) at steady-state (ng x h / mL)
Cmax	The maximum (peak) observed plasma, blood, serum, or other body fluid drug concentration after single dose administration (ng / mL)
Tmax	The time to reach maximum (peak) plasma, blood, serum, or other body fluid drug concentration after single dose administration (h)

The PK profile of MHV370 will be characterized but not limited to the PK parameters listed above.

Arithmetic mean (SD) and geometric mean (95% CI) plasma concentration data will be plotted across time, with separate line types for treatment.

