3.1 Primary endpoint(s)

SjS

A total of approximately 48 participants with SjS will be randomized in a 1:1 ratio to MHV370 or placebo, with the aim to have at least 40 participants completing Week 24 assessment.

With 40 participants in the analysis of the primary efficacy variable (20 in MHV370 and 20 in placebo), the study would have approximately 80% chance of meeting both efficacy criteria, when the true difference between MHV370 and placebo is 3.5 points. In case the difference between MHV370 and placebo is zero points, the study would have approximately 10 % chance of meeting both efficacy criteria.

These calculations are based on assumed standard deviation of 5.1 in change from baseline in ESSDAI, based on data from TEARS study with rituximab (Devauchelle-Pensec et al 2014).

MCTD

A total of approximately 12 participants with MCTD will be randomized in a 1:1 ratio to MHV370 or placebo. The sample size was chosen for logistical reasons and no sample size calculations were made.

4 Change to protocol specified analyses

No change from protocol specified analysis was made.

5 Appendix

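### The Week 4 AUClast stops at 4 h for most sites and at 6 h for selected sites, and SAP 2.8 pools the two without a common time window

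*Protocol*

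**What the plan says.** - **Sampling.** Protocol section 3 (Treatment) and Table 8-1 schedule Week 4 samples pre-dose and at 0.5, 1, 2 and 4 h for all participants. Section 3 adds: "At Week 4, an additional PK sample will be taken at 6 hours post dose, at selected sites". Footnote 3 of Table 8-1 marks the 6 h column "Only at selected sites".
- **Parameters.** Protocol 8.5.1 gives the Week 4 set as "Phoenix WinNonlin (Version 6.4 or higher): Cmax, Tmax, AUClast", derived from actual sampling times, and allows more: "Additional PK parameters may be added to further characterize the dose/exposure relationship or refine PK/PD analysis".
- **Definitions.** Protocol Table 12-1 and SAP 2.8 define AUClast as running from time zero to the last measurable sample. Both also list AUC0-t, to a specified time t, and AUCtau, to the end of the dosing interval. Neither document gives t a value, assigns AUC0-t or AUCtau to a visit, or says how AUCtau would be derived.
- **Summaries.** SAP 2.8 states: "Descriptive summary statistics for pharmacokinetic parameters will be provided by treatment separately and combined for SjS and MCTD subjects". It has no rule on last sampling time.
- **Changes.** SAP section 4 states: "No change from protocol specified analysis was made".

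**The concern.** AUClast compares across participants only if they share a sampling horizon. Here the horizon depends on the site. A participant at a selected site accumulates two more hours of exposure than an identical participant elsewhere, and both values enter the same row of the PK table under the same name.

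AUC is a named endpoint of the secondary PK objective. Its reported level would depend on how many MHV370 participants attended a 6 h site. The SjS and MCTD summaries could differ for the same reason: with about 6 MCTD participants on active drug (12 randomized 1:1), the result hangs on where each was enrolled. Any graphical PK/PD plot using AUClast would inherit the problem.

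**Working it through.** **Tracing the rule.** The documents state no AUC figure, so there is none to reproduce.

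1. Last scheduled Week 4 sample: 4 h at all sites, 6 h at selected sites.
2. The upper limit of AUClast is the participant's own last measurable sample.
3. If the last scheduled sample is taken and is at or above the LLOQ (anticipated 1.0 ng/mL), AUClast equals AUC0-6h at selected sites and AUC0-4h elsewhere. Otherwise the limit is earlier still.
4. SAP 2.8 summarises by treatment and indication, and then combined. No step brings the two windows together.

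**Size, under stated assumptions.** From the documents: a dosing interval tau of about 12 h and the sampling times above. Assumed: one compartment with first-order absorption at steady state, ka 0.7-1.5 per h, half-life 2-12 h, and shares of 6 h participants of 10%, 25% and 50%.

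With ke = ln 2 / half-life, the steady-state curve, up to a constant, is

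C(t) = ka/(ka − ke) × [e^(−ke·t)/(1 − e^(−ke·tau)) − e^(−ka·t)/(1 − e^(−ka·tau))].

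Integrating the same curve to 4 h and to 6 h (arbitrary units):

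| ka (per h) | half-life (h) | AUC0-4 | AUC0-6 | Ratio, exact | Ratio, linear trapezoid at planned times |
|---|---|---|---|---|---|
| 1.5 | 2 | 1.994 | 2.469 | 1.238 | 1.251 |
| 0.7 | 12 | 6.323 | 9.519 | 1.506 | 1.510 |

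These are the extremes of the assumed range. For an identical profile, the 6 h sites report an AUClast 24-51% higher.

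For a share p of 6 h participants and ratio r (1.238 to 1.506):

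- Arithmetic mean shift = p × (r − 1).
- Geometric mean shift = r^p − 1.
- Geometric CV = √(exp(ln(1 + 0.40²) + p(1 − p)(ln r)²) − 1), from an assumed 40%.

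| Share p | Arithmetic mean | Geometric mean | Geometric CV (from 40%) |
|---|---|---|---|
| 10% | +2.4 to +5.1% | +2.2 to +4.2% | 41-42% |
| 25% | +5.9 to +12.6% | +5.5 to +10.8% | 41-44% |
| 50% | +11.9 to +25.3% | +11.3 to +22.7% | 42-46% |

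**MCTD.** One 6 h participant among 6 on active drug shifts the mean by (r − 1)/6: 0.238/6 = 4.0% to 0.506/6 = 8.4%.

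**Actual times.** Ending the integral 15 minutes before or after 4 h changes it by about 4-7% in either direction. A fixed window therefore also needs a rule for samples not drawn exactly at 4 h.

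**Sensitivity to the assumed kinetics.** Faster kinetics shrink the effect: with ka 3 per h the exact ratio is 1.20 at a half-life of 2 h and 1.07 at 1 h. With one common window the ratio between site types is 1.00 by construction.

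**The case against.** The best counter-argument is that little depends on this. PK is summarised descriptively in one active arm at one dose. No PK test, decision rule or formal SjS-versus-MCTD comparison is planned, and PK/PD work is optional. SAP 2.8 lists concentrations and parameters by participant, so AUC0-4h could be calculated later. Concentration summaries are by time point and do not mix windows. Weeks 12 and 24 use concentrations only. AUC0-t and AUCtau are already in the parameter list. Protocol 8.5.1 has redacted blocks, and SAP Table 5-3 has no readable content, so a rule could sit out of sight. The percentages rest wholly on assumed kinetics.

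Most of this stands as a limit on importance. The effect on spread is small, and 24-51% is an illustration, not a bound. It does not remove the defect. Recoverability from listings does not make the planned table correct, and AUC0-t cannot serve as the pooled measure while t is unset and nothing designates it. AUCtau would need an unstated assumption, because no sample is scheduled after 6 h. The redactions limit certainty, but the readable summary rule in SAP 2.8 sets no common window.

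**Conclusion.** The concern holds. As written, the plan puts AUC0-4h and AUC0-6h under one label and averages them. The mixing follows from the sampling schedule and the definition of AUClast, provided the last scheduled sample is taken and quantifiable. Its size cannot be known from the documents: over the assumed kinetics and shares, the pooled arithmetic mean is raised by between about 2% and 25%.

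The consequence is confined to the Week 4 AUC summary and any optional PK/PD use of AUClast. Primary efficacy is unaffected, as is a population model fitted to concentrations. It should be corrected, but it does not threaten the trial's main conclusion. The remaining uncertainty is whether redacted text already contains a window rule.

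**What to change.** In SAP 2.8:

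- Set t = 4 h for AUC0-t and name AUC0-4h as the Week 4 AUC for the SjS, MCTD and combined summaries.
- State how AUC0-4h is obtained when the actual sample is not at exactly 4 h, for example by interpolation or extrapolation to 4 h.
- Keep AUClast, since Protocol 8.5.1 names it, but only in listings or summarised split by last sampling time.
- Report AUC0-6h for the 6 h subset alone.
- If AUCtau is reported, state the assumption behind it, such as using the pre-dose value as the 12 h value, or a population model.

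Add a line to SAP section 4, which now records no change from the protocol's analysis. The cost is a few lines of text. Protocol 8.5.1 already permits added parameters, and no new samples are needed. The drawback is that the pooled AUC covers 4 of about 12 hours and leaves out the 6 h point, which remains available in the subset summary and the listings.
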